8.4 Analyses

8.4.1 Demographic and baseline characteristics : Demographic and baseline characteristics will be summarised using summary statistics based on the ITT data set, for each treatment group as well as for all patients combined. Key baseline characteristics will be summarised. No statistical test will be performed for comparison of any baseline measurement among treatment groups. Demographic and baseline characteristics will be summarised for the total study population.

8.4.2 Efficacy Analysis: Between groups comparisons will be made using two-way analysis of variance (ANOVA.) to analyze changes in hepatic/myocardial fat following saxagliptin

treatment in comparison to placebo (primary efficacy analysis). Secondary efficacy analysis will include the effect of saxagliptin (versus placebo) on LV function and monocyte inflammation. Pre and post treatment within a group will be analyzed using paired t-tests. Simple correlation analysis will be performed with Pearson's correlation coefficients to examine the relationship between hepatic fat and myocardial fat/ LV function . Spearman Rank Correlation will be used for data which is not normally distributed. All statistical analysis will be performed using SAS (Cary, NC).

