Statistics:	Between groups (i.e., saxagliptin therapy vs. placebo) comparisons will be made using two-way analysis of variance (ANOVA). Pre and post treatment within a group will be analyzed using paired t-tests. Simple correlation analysis will be performed with Pearson's correlation coefficients to examine the relationship between hepatic fat and myocardial fat and LV function. Multivariate analysis will be performed where appropriate to examine the impact of simultaneous changes (glucose levels) in experimental parameters on hepatic fat. All statistical analysis will be performed using SAS (Cary, NC). Sample size is calculated using SigmaPlot software (San Jose, CA). For the two major outcome variables i.e. myocardial fat and hepatic fat, the sample size of ~ 16 patients per treatment group (total of 32 patients) will have >90% power to detect a difference in the means of 20%, assuming a standard deviation of 15%, and with alpha= 0.025. Given that we expect about 10-15% of the patients enrolled may not complete the 6 month study, we would like to enroll 36 patients so that 32 patients may complete the study.

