Following determination of eligibility, 40 IGT or prediabetes subjects will be randomized (double blind) to participate in one of the following two treatment arms (i) saxagliptin 5 mg daily PO for 26 weeks or (ii) Placebo PO daily for 26 weeks (control arm). Two weeks prior to randomization, subjects will meet with a dietitian and will be instructed to consume a weight-maintaining diet containing 50% carbohydrate, 30% fat, and 20% protein. During the week prior to start of the study all subjects will receive: (i) baseline measurements of FPG, plasma adiponectin (HMW and total adiponectin), CRP, IL-1, IL6, TNF-alpha, MMP-9, ICAM, VCAM, Fibroblast Growth Factor 21 (FGF21), fasting

plasma lipids, postprandial plasma triglyceride level (at 2 hours following a mixed meal), and HbA1c; (ii) monocyte isolation from peripheral (venous) whole blood and quantification of monocyte TLR2, TLR4, SOCS-3, MYD88, NFkappaB (P65) and Ikb-alpha, and Ikb-beta protein as well as expression levels of CD36, MCP-1, MMP-9, VCAM1, ICAM1 and JNK. We will also measure of plasma lipopolysaccharide (LPS) and LPS- binding protein (LPS-BP) concentrations. Plasma samples used for LPS determination will be stored in LPS-free glass tubes to prevent loss of endotoxin to plastic tube walls. All materials for the assay will be rendered LPS-free; and (iii) liver and myocardial fat content with magnetic resonance (MR) spectroscopy and determination of left ventricular systolic and diastolic function by MR imaging as detailed below.

During the entire 6 month treatment period, subjects will return to the Clinical Research Center every 4 weeks at 0800 h following an overnight fast for measurement of FPG, body weight, and blood pressure. A urine pregnancy test will also be performed at each visit. On each visit, dietary adherence will be reinforced by the dietician. Fasting plasma lipids and postprandial triglyceride levels, HbA1c, and LFTs will be measured at 3 months and at the end of the 6 month study period. At the end of the treatment period of six months all subjects will also undergo a repeat 75 gram OGTT (for measurements of baseline FPG, and plasma glucose, FFA, c-peptide and insulin during OGTT as well as 2 hour plasma triglyceride measurements as described previously), plasma adiponectin,

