CRP, IL-1, IL6, TNF-alpha, MMP-9, ICAM, VCAM, Fibroblast Growth Factor 21 (FGF21), FFA, insulin, LPS and LPS-BP. Liver and Myocardial fat and LV function as well as monocyte studies for inflammatory pathways as detailed previously will be repeated after 26 weeks of therapy.

Measurement of Liver Fat Content (MR Spectroscopy)

Localized ¹H nuclear magnetic resonance spectra of the liver will be obtained on a 3.0 Tesla magnetic resonance imaging scanner (Department of Radiology, St Lukes Episcopal Hospital and Texas Heart Institute, Houston) using a standard body coil in transmitter and receiver mode. An initial T1-weighted spin-echo anatomical magnetic resonance scan for liver MRS localization will be performed with the following parameters: repetition time/echo time = 130 msec/15 msec; 160 degrees; slice thickness = 7 mm; field of view = 44 cm x 45 cm; number of excitations = 1; and an image matrix = 100 x 256. The slice with the largest gross dimensions of the liver will be chosen for the MRS study. MRS for water and fat quantification will be accomplished by using a point resolved spectroscopy sequence as described previously (3). The imaging parameters for point resolved spectroscopy sequence are as follows: repetition time/echo time = 1500 msec/54 msec; 90 degree; number of averages = 2; and data points = 512. A 3 cm x 3 cm x 3 cm volume (voxel) will be selected in the left, right anterior, and right posterior hepatic lobes for scanning to provide a more generalized distribution of fat within the liver. During the measurements, the

subject will be supine within the bore of the magnet. The total scan time is approximately 60 min. During the MRS examinations, identical areas of the liver are scanned in the pre- and post-treatment MRS studies of the same subject by the use of anatomical landmarks visualizing images.

After line broadening, phase and baseline correction, the peak area of the water at 4.77 ppm, and fat resonance (Sf) at 1.4 ppm will be measured. Quantification of the fat content will be done by comparing the area of the Sf with that of the unsuppressed water. Spectroscopic data will be processed using the operating system software. Hepatic fat percentage will be calculated by dividing $(100 \times \text{Sf})$ by the sum of Sf and peak area of the water. This technique is highly reproducible, with a coefficient of variation less than 2% when the same subjects were studied on eight separate days.

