8 STATISTICAL CONSIDERATIONS

8.1 Sample size determination

Sample size is calculated using SigmaPlot software (San Jose, CA). For the two major outcome variables i.e. myocardial fat and hepatic fat, the sample size of ~ 16 patients per treatment group (total of 32 patients) will have >90% power to detect a difference in the means of 20%, assuming a standard deviation of 15%, and with $\alpha = 0.025$. Given that we expect about 20% of the patients enrolled may not complete the 6 month study, we would like to enroll 40 patients so that 32 patients may complete the study.

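### The primary comparison of change in hepatic and myocardial fat omits the baseline scan as a covariate; ANCOVA would move power from 91.5% to between 90.5% and 98.4%, depending on a pre/post correlation the plan does not give

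*Combined protocol and SAP*

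**What the plan says.** Section 8.4.2 gives the primary efficacy analysis: "Between groups comparisons will be made using two-way analysis of variance (ANOVA.) to analyze changes in hepatic/myocardial fat following saxagliptin" treatment, relative to placebo. The Statistics row of the synopsis agrees: "Between groups (i.e., saxagliptin therapy vs. placebo) comparisons will be made using two-way analysis of variance (ANOVA"). Neither place names the two factors of the ANOVA, and neither enters baseline fat as a covariate.

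The only multivariable analysis is in the synopsis: "Multivariate analysis will be performed where appropriate to examine the impact of simultaneous changes (glucose levels) in experimental parameters on hepatic fat". It concerns changes that occur after randomisation and does not adjust for the baseline scan.

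The baseline value will exist. Section 4.1 lists "liver and myocardial fat content with magnetic resonance (MR) spectroscopy" among the measurements in the week before the study starts, and says of the end of treatment: "Liver and Myocardial fat and LV function as well as monocyte studies for inflammatory pathways as detailed previously will be repeated" after 26 weeks. The schedule in section 6.1 puts the MRI studies at Visit 3 (week -1) and Visit 11 (week 26).

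Section 8.1 says that about 16 patients per group "will have >90% power to detect a difference in the means of 20%, assuming a standard deviation of 15" per cent, at alpha 0.025. It does not give the sidedness of alpha or a pre/post correlation, and does not say whether 15% is the SD of change or of a single scan.

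On the other analyses, 8.4.2 says: "Secondary efficacy analysis will include the effect of saxagliptin (versus placebo) on LV function and monocyte inflammation", and "Pre and post treatment within a group will be analyzed using paired t-tests".

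**The concern.** A change score uses the baseline, but with its slope fixed at 1. ANCOVA estimates the slope from the data, so its residual variance cannot exceed the variance of the change. It also takes chance baseline imbalance out of the treatment estimate, which the change score does not do. When the true slope is below 1, an arm that starts high by chance tends to fall further for reasons unrelated to treatment, and the change score counts that fall as treatment effect.

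Both primary endpoints are affected. With about 16 completers per arm, baseline differences of half an SD are not rare, and section 5.3 describes no stratification on baseline fat. Adjustment is most convincing when it is specified in advance; added after unblinding, it could look data-driven.

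**Working it through.** **Inputs from the documents.** Section 8.1: n = 16 per arm, difference 20, SD 15, alpha 0.025, stated power above 90%. Sections 4.1 and 6.1: scans at weeks -1 and 26.

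**Assumptions, because the documents are silent.** 15 is the SD of change; additive scale; equal pre and post variances; common slope in both arms; alpha two-sided unless noted; correlation rho between 0.3 and 0.99.

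**Step 1: reproduce the plan's figure.** Two-sample t-test on change:

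- standard error = 15 × √(2/16) = 5.303
- noncentrality = 20 / 5.303 = 3.771, with 30 df
- power = 91.5% two-sided (95.4% if alpha 0.025 is one-sided)

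The stated figure is confirmed. If the two-way ANOVA is group by time, its interaction test is this same test.

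**Step 2: ANCOVA.** With scan SD s, the variance of change is 2s²(1 - rho) = 225, and the ANCOVA residual variance is s²(1 - rho²) = 225 × (1 + rho)/2. Power is noncentral t with 29 df, averaged over the random baseline difference by multiplying the variance by 1 + F(1,30)/30.

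| rho | residual SD | ANCOVA, two-sided | ANCOVA, one-sided |
|---|---|---|---|
| 0.3 | 12.09 | 98.4% | 99.3% |
| 0.5 | 12.99 | 96.7% | 98.5% |
| 0.7 | 13.83 | 94.5% | 97.2% |
| 0.8 | 14.23 | 93.2% | 96.5% |
| 0.9 | 14.62 | 91.8% | 95.6% |
| 0.95 | 14.81 | 91.1% | 95.2% |
| 0.99 | 14.96 | 90.5% | 94.8% |
| planned change score | 15 | 91.5% | 95.4% |

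Simulation with 60,000 trials per rho agrees to within about 0.1 point for ANCOVA. Type I error was 2.4-2.6% for both methods.

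**Step 3: the floor.** Without the equal-variance assumption, the residual variance is still at most 225. ANCOVA power is therefore at least 90.3% two-sided, or 94.7% one-sided. The largest loss is 91.5 - 90.3 = 1.2 points (95.4 - 94.7 = 0.7 one-sided).

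**Step 4: equivalent sample size.** At rho 0.5, ANCOVA with 16 per arm has 96.73%. The unadjusted test has 96.66% with 20 per arm and 97.4% with 21, so about 21 are needed to match it.

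**Step 5: other readings of 8.1 (two-sided).**

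- 15 is the SD of one scan: unadjusted 79/91/99%, ANCOVA 93/97/99.6% at rho 0.3/0.5/0.7.
- 20% and 15% are relative, taken as ln(0.8) and 0.15 on the log scale: unadjusted 96.3%, ANCOVA 99.6/99.0/97.9/96.5/95.7% at rho 0.3/0.5/0.7/0.9/0.99.

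**Step 6: chance imbalance.** The baseline difference has standard error √(2/16) = 0.354 SD. The probability that the saxagliptin arm starts more than 0.5 SD higher is P(Z > 1.414) = 7.9%, and the mean difference in those trials is 0.66 SD. The change score then overstates benefit by (1 - rho) × 0.66 × baseline SD, where baseline SD = 15/√(2(1 - rho)). At rho 0.5 that is 0.5 × 0.66 × 15, or about 4.9 points. For rho 0.3/0.5/0.7/0.8/0.9/0.95 the shifts are 5.9/4.9/3.8/3.1/2.2/1.6 points. In simulation the ANCOVA shift stayed within 0.14 of zero.

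**The case against.** The strongest objection is that nothing is broken. The planned test is unbiased over repeated trials, holds its type I error and reaches the promised power, and baseline is already used by subtraction. All of that is true, and it is why this is a point about precision.

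The gain also rests on a correlation the documents do not give. Section 4.1 reports a coefficient of variation below 2% for repeated liver spectroscopy. Subjects must be weight-stable, on a weight-maintaining diet and on fixed lipid-lowering doses. For hepatic fat these features favour a higher correlation, where little power is gained. They do not establish the 26-week correlation, and no such figure is given for myocardial fat. This stands as a reason to show a range and not to promise a particular gain.

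The lower end of the range is strained on the additive scale. With equal variances, a change SD of 15 at rho 0.99 implies a baseline SD of 15/√0.02 = 106 points, which is impossible for hepatic fat expressed as a percentage bounded at 100. That end is best read as an arithmetic limit. The 90.3% floor does not depend on equal variances and still bounds the cost.

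Imbalance works both ways. By symmetry, about another 8% of trials would understate benefit, and at rho 0.7 or above the shifts are below one standard error (5.3). This is already counted in the type I error. It does not change the case for removing a known source of error from the estimate of the trial actually run.

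Finally, the undefined factors of the two-way ANOVA are a gap in their own right. The 91.5% comparator assumes the change-score reading.

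**Conclusion.** The point holds as an improvement that should be made, not as an error in the plan. Under the main assumptions and two-sided alpha, ANCOVA gains about 7 points of power at rho 0.3, 5 at 0.5 and 3 at 0.7. It gains essentially nothing by 0.9-0.95 and loses about 1 point near 1. If alpha is one-sided, the gain at rho 0.5 is about 3 points (95.4% to 98.5%). If 15 is the SD of a single scan, the gain at low correlation is larger (79% to 93% at rho 0.3). On every reading the loss is bounded at about 1 point, and ANCOVA protects both primary endpoints against chance baseline imbalance. Confidence in the size of the gain is only medium, because rho, the sidedness of alpha and the scale of the 20% and 15% are all unstated.

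**What to change.** Replace the between-group analysis in 8.4.2 and in the synopsis with text such as:

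> For each efficacy endpoint (hepatic fat and myocardial fat as primary, each at the planned alpha of 0.025; LV function and monocyte measures as secondary), the week-26 value will be compared between arms by ANCOVA, with treatment as factor and the pre-treatment (Visit 3) value of the same endpoint as covariate. The adjusted difference will be reported with a confidence interval that matches the planned alpha. Within-arm paired t-tests are descriptive.

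Analyse on the scale on which the 20% and 15% of section 8.1 are defined, and state that scale. This wording also replaces a two-way model whose factors are not named with one that can be reproduced. The power figures here were worked out for the two primary endpoints only; the secondary endpoints are included so that one model is used throughout.

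The cost is a change of wording, one degree of freedom per model, and at worst about 1 point of power (91.5% to 90.3% two-sided, 95.4% to 94.7% one-sided).

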1.3 Research Hypothesis

We hypothesize that saxagliptin therapy (compared to placebo) would be associated with a reduction in myocardial and hepatic fat content, an improvement in left ventricular function, and a reduction in monocyte inflammation in patients with impaired glucose tolerance.

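### The planned simple correlation of hepatic fat with myocardial fat and LV function has no treatment-arm term and no stated time point; run across both arms on change or week-26 values, it partly re-reports the drug effect

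*Combined protocol and SAP*

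**What the plan says.** Section 8.4.2 (Efficacy Analysis) states: "Simple correlation analysis will be performed with Pearson's correlation coefficients", and gives the aim as "to examine the relationship between hepatic fat and myocardial fat/ LV function". It adds a fallback: "Spearman Rank Correlation will be used for data which is not normally distributed". The Statistics entry of the Protocol Synopsis gives the same method and almost the same aim, "to examine the relationship between hepatic fat and myocardial fat and LV function", without the Spearman fallback.

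Neither place names treatment arm as a covariate or stratum. Neither says which values enter the correlation: baseline, week 26, or change. By contrast, the sentence just before it in 8.4.2 names the grouping explicitly: "Pre and post treatment within a group will be analyzed using paired t-tests".

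The synopsis also mentions a further model: "Multivariate analysis will be performed where appropriate to examine the impact of simultaneous changes (glucose levels) in experimental parameters on hepatic fat". It names glucose, not arm, and does not reappear in 8.4.2.

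**The concern.** Section 1.3 expects saxagliptin to produce "a reduction in myocardial and hepatic fat content, an improvement in left ventricular function". Every variable in the correlation is therefore one that the drug is hypothesised to move. If change or week-26 values from both arms go into one unadjusted coefficient, arm is a common cause of both variables. Treated patients tend to sit at one end of both scales and placebo patients at the other, so a correlation appears even if, among patients on the same treatment, a larger fall in liver fat says nothing about heart fat.

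At stake is how a supportive result is read. A significant coefficient could be taken to show that the two organs respond together in individual patients, when it reflects only that the drug acted on each. The primary and secondary between-group comparisons do not depend on it.

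**Working it through.** **Inputs from the documents.** Section 8.1 sizes the trial "to detect a difference in the means of 20" percent, with SD 15%, alpha 0.025, about 16 completers per arm (32 in total) and power above 90%, for both myocardial and hepatic fat. It enrols 40 to allow for 20% dropout.

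**Assumptions made here.** Two-sided testing of correlations at 0.05 (the documents give no level); 1:1 arms; normal data; zero correlation within arms; the 15% SD applies to the quantity being correlated (8.1 does not say whether it is the SD of levels or of changes); any effect below 1.33 SD; and any effect at all on LV function, for which no size is given.

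**Step 1: the plan's own figure.** Standardised effect d = 20/15 = 1.33. Noncentrality = 1.333/√(2/16) = 3.77 on 30 degrees of freedom. At two-sided alpha 0.025 the t-test has power 0.915 (normal approximation 0.937). Enrolment: 32/(1 − 0.20) = 40. Section 8.1 reproduces. The plan gives no figure for the correlation.

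**Step 2: correlation induced by arm alone.** With equal arms the arm indicator has variance 1/4. Effects d1 and d2 (in within-arm SDs) therefore add d1·d2/4 to the covariance, and d1²/4 and d2²/4 to the two variances:

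r = (d1·d2/4) / √[(1 + d1²/4)(1 + d2²/4)]

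For d1 = d2 = 1.333: d²/4 = 0.444, so r = 0.444/1.444 = 0.308.
For d1 = d2 = 1: r = 0.25/1.25 = 0.200.
For d1 = 1.333, d2 = 0.667: r = 0.222/√(1.444 × 1.111) = 0.222/1.267 = 0.175.

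**Step 3: how often p<0.05 results.** Simulated Pearson tests with 16 per arm and zero within-arm correlation (50,000 trials per row; 40,000 for the 1 SD row):

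| Effect on first measure (SD) | Effect on second (SD) | Induced r | p<0.05, unadjusted | p<0.05, arm-adjusted |
|---|---|---|---|---|
| 1.33 | 1.33 | 0.308 | 42.8% | 4.9% |
| 1.00 | 1.00 | 0.200 | 20.3% | 5.1% |
| 1.33 | 0.67 | 0.175 | 16.5% | 4.9% |
| 0.67 | 0.67 | 0.100 | 8.2% | 5.1% |
| 1.33 | 0.33 | 0.091 | 7.8% | 4.9% |
| 0.33 | 0.33 | 0.027 | 5.3% | 5.1% |
| 1.33 | 0 | 0 | 5.0% | 4.9% |

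If all 40 enrolled patients contributed (20 per arm), the first row would be 52.1% against 4.9%.

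**Step 4: sign.** r takes the sign of d1·d2. If both fat measures fall, the induced correlation is positive. If fat falls while an LV measure on which higher is better rises, it is negative.

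**The case against.** The strongest reply is that the documents do not commit to the analysis that fails. They do not say that the arms are pooled. The correlation sentence also omits the word changes, which 8.4.2 does use for the primary comparison, so it could mean baseline levels, which no treatment can affect. Correlations run separately by arm would be safe too. This stands, and the finding is conditional for that reason. It does not remove the point: the stated method is a simple correlation with no arm term, in a section that names the grouping where by-group analysis is meant.

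Second, if the drug moves both measures, the pooled variables really are correlated across the trial population, so rejecting zero is not an error for that null. This also stands. The 43% is an error rate only if the target is association within arms, and the plan does not name its target. But a coefficient that merely restates two treatment effects adds little to the between-group comparisons.

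Third, the 43% needs 1.33 SD on both measures, which is a power assumption. The table shows how quickly the rate falls, and nothing in the documents lets the 43% be applied to LV function.

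The synopsis's multivariate analysis is not an answer, because it names glucose rather than arm and is to be done only where appropriate.

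Two stronger readings go beyond the documents. A reader might infer that pre- and post-treatment values would be stacked as separate rows, counting patients twice; no section proposes this, and 8.4.2 treats pre/post data as paired. A reader might also infer that the correlation carries the trial's mechanistic claim; it appears in neither the hypothesis, the objectives, the efficacy assessments nor the endpoint definitions.

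**Conclusion.** The point holds conditionally, as a cheap improvement. If the correlation is run across both arms on change or week-26 values, the design effect on both fat measures gives an expected r of about 0.31 with no association within arms, and p<0.05 in about 43% of trials with 32 completers, against about 5% with arm adjustment. The excess is modest for smaller effects and absent if only one measure moves. These rates rest on the 0.05 level, zero within-arm correlation, normal data and the reading of the 15% SD set out above; they were computed for Pearson, though the Spearman fallback equally lacks an arm term. For LV function the documents support only the mechanism, not a size.

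It would be wrong to conclude that the plan certainly ignores arm, or that the trial's efficacy conclusions are at risk. Baseline-only and by-arm correlations are unaffected, as are the primary and secondary treatment comparisons.

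**What to change.** In 8.4.2 and in the synopsis Statistics entry, replace the simple correlation with two specified analyses:

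- a partial correlation (Pearson, or Spearman where the data are not normal) of the week-26 changes in hepatic fat with those in myocardial fat and in each LV measure, adjusted for treatment arm, with one row per patient;
- a separate correlation of the baseline values, reported as such.

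Arm is already recorded and no new data are needed. The cost is a change of wording and one degree of freedom: with 32 completers, 29 (32 − 3) instead of 30 (32 − 2). In every scenario simulated, the adjusted correlation kept its rate at about 5%. The same wording settles which time point is meant.
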